**Table 4: Biomarker sampling timepoints, Parts 1 and 2**

Cycle	Study Day	Time	Window	Relative Time	Flow Cytometry	Plasma and Serum Cytokines	Serum Biomarkers	RNA	PBMC	TCR
1	Day 1	Predose	Within 24 hr prior to start of brentuximab vedotin infusion	Start of brentuximab vedotin infusion	X	X	X	X	X	X
	Day 2 a	24 hr postdose	±4 hr	Start of brentuximab vedotin infusion		X	X	X		
	Day 8	Predose	Within 24 hr prior to start of nivolumab infusion	Start of nivolumab infusion	X	X	X	X	X	X
	Day 15	336 hr postdose	±24 hr	Start of brentuximab vedotin infusion	X	X	X	X	X	X
2	Day 1	Predose	Within 24 hr prior to start of brentuximab vedotin infusion	Start of brentuximab vedotin infusion	X	X	X	X	X	X
	Day 8 b	168 hr postdose	±24 hr	Start of brentuximab infusion	X	X	X			
3	Day 1	Predose	Within 24 hr prior to start of brentuximab vedotin infusion	Start of brentuximab vedotin infusion	X	X	X	X	X	X
4	Day 1 a	Predose	Within 24 hr prior to start of brentuximab vedotin infusion	Start of brentuximab vedotin infusion	X	X	X	X	X	X
	Day 2 a	24 hr postdose	±4 hr	Start of brentuximab vedotin infusion		X	X	X		
	Day 8 a	168 hr postdose	±24 hr	Start of brentuximab vedotin infusion	X	X	X	X	X	X
	EOT	30 + 7 days post last dose of study drug(s)			X	X	X	X	X	X

a For patients in Part 1 only

b For patients in Part 2 only

**Table 5: Biomarker sampling timepoints, Part 3**

Cycle	Study Day	Time	Window	Relative Time	Flow Cytometry	Plasma and Serum Cytokines	Serum Biomarkers	RNA	PBMC	TCR
1	Day 1	Predose	Within 24 hr prior to start of brentuximab vedotin infusion	Start of brentuximab vedotin infusion	X	X	X	X	X	X
	Day 8	168 hr postdose	±24 hr	Start of brentuximab vedotin infusion	X	X	X	X	X	X
	Day 15	336 hr postdose	±24 hr	Start of brentuximab vedotin infusion	X	X	X	X	X	X
2	Day 1	Predose	Within 24 hr prior to start of brentuximab vedotin infusion	Start of brentuximab vedotin infusion	X	X	X	X	X	X
	Day 8	168 hr postdose	±24 hr	Start of brentuximab infusion	X	X	X			X
3	Day 1	Predose	Within 24 hr prior to start of brentuximab vedotin infusion	Start of brentuximab vedotin infusion	X	X	X	X	X	X
EOT			30 + 7 days post last dose of study drug(s)		X	X	X	X	X	X

#### **7.4.1 Tumor Biopsies**

Formalin fixed paraffin-embedded tumor tissue blocks taken after relapse of prior therapy will be collected at screening to assess biomarkers implicated in sensitivity or resistance to brentuximab vedotin and/or nivolumab (e.g., CD30 expression, PD-L1/L2 amplification, and expression). If tumor tissue block is not available, a minimum of approximately 20 unstained charged slides of the tumor tissue will be required. If multiple blocks are available, the one with the highest tumor content is preferred. If archival tumor tissues (i.e., tumor tissue obtained at the time of the patient's original diagnosis and/or at the time of subsequent procedures conducted as part of the patient's standard care) are available, they will be collected under the same criteria to understand the impact of prior treatment on CD30 and PD-L1/L2 expression. If any tissue remains, the tumor pathology block may be returned to the original site by the Sponsor or designee at the end of the study upon request. See the Laboratory Manual for details.

Efforts should be made to take additional biopsies in patients who demonstrate disease progression, indeterminate response on study, or residual disease at the EOT visit. These optional samples are to be tested for the expression of CD30 and PD-L1/L2 expression and other potential markers to understand potential delayed response and/or resistance mechanism.

Assessments may include histopathology and immunohistochemistry of tumor biopsies for:

- Expression of PD-L1/L2, CD30, immune cell markers and expression of other immune checkpoint molecules in malignant Reed-Sternberg cells and tumor infiltrating lymphocytes by IHC, as well as amplification of 9p24.1
- Tumor infiltrating lymphocytes (CD3, CD4, CD8, Foxp3+ and ratios thereof)
- Expression of CD30 and PD-1 among T, B, macrophage and myeloid cell populations including, but not limited to CD4, CD8, Foxp3, CD68, and CD163
- Amplification and expression of PD-L1 and PD-L2 by malignant Reed-Sternberg cells and tumor infiltrating lymphocytes
- Expression (by RNA or protein) of other immune checkpoint molecules, including, but not limited to Galectin-1, if an assay becomes available
- Epstein-Barr Virus infection status if not previously known
- Expression analysis of 23-gene predictor for outcome post-ASCT in classical HL

#### **7.5 Biospecimen Repository**

In the US only, for patients who provide additional consent, remaining de-identified unused blood and/or tissue will be retained by Seattle Genetics and used for future research, including but not limited to the evaluation of targets for novel therapeutic agents, the biology of ADC sensitivity and resistance mechanisms, and to identify pharmacodynamic biomarkers of ADCs. Blood and tissue samples donated for future research will be retained for a period of up to 25 years. If additional consent is not provided, any remaining biological samples will be destroyed following study completion.

## 7.6 Safety Assessments

The assessment of safety during the course of this study will consist of the surveillance and recording of adverse events (AEs) including serious adverse events (SAEs), recording of concomitant medication and measurements of protocol-specified physical examination findings, pulse oximetry tests, and laboratory tests.

Safety will be monitored over the course of the study by an SMC as described in Section 9.3.9.

### 7.6.1 Adverse Events

#### 7.6.1.1 Definitions

##### Adverse Event

According to the International Council for Harmonisation (ICH) E2A guideline Definitions and Standards for Expedited Reporting, and 21 CFR 312.32, Investigational New Drug (IND) Safety Reporting, an AE is any untoward medical occurrence in a patient or clinical investigational subject administered a medicinal product and which does not necessarily have a causal relationship with this treatment.

The following information should be considered when determining whether or not to record a test result, medical condition, or other incident on the Adverse Events and Pre-existing Conditions CRF:

- From the time of informed consent through the day prior to study Day 1, only study protocol-related AEs should be recorded. A protocol-related AE is defined as an untoward medical event occurring as a result of a protocol mandated procedure.
- All medical conditions present or ongoing predose on study Day 1 should be recorded.
- All AEs (regardless of relationship to study drug) should be recorded from study Day 1 (predose) through the end of the safety reporting period (see Section 7.6.1.3). Complications that occur in association with any procedure (e.g., biopsy) should be recorded as AEs whether or not the procedure was protocol mandated.
- Changes in medical conditions and AEs, including changes in severity, frequency, or character, during the safety reporting period should be recorded.
- In general, an abnormal laboratory value should not be recorded as an AE unless it is associated with clinical signs or symptoms, requires an intervention, results in a SAE, or results in study termination or interruption/discontinuation of study treatment. When recording an AE resulting from a laboratory abnormality, the resulting medical condition rather than the abnormality itself should be recorded (e.g., record “anemia” rather than “low hemoglobin”).

## **Serious Adverse Events**

An AE should be classified as an SAE if it meets one of the following criteria:

Fatal:	AE resulted in death
Life threatening:	The AEs placed the patient at immediate risk of death. This classification does not apply to an AE that hypothetically might cause death if it were more severe.
Hospitalization:	The AE required or prolonged an existing inpatient hospitalization. Hospitalizations for elective medical or surgical procedures or treatments planned before the signing of informed consent in the study or routine check-ups are not SAEs by this criterion. Admission to a palliative unit or hospice care facility is not considered to be a hospitalization. Hospitalizations or prolonged hospitalizations for scheduled therapy of the underlying cancer or study target disease need not be captured as SAEs.
Disabling/incapacitating:	Resulted in a persistent or significant incapacity or substantial disruption of the patient's ability to conduct normal life functions.
Congenital anomaly or birth defect:	An adverse outcome in a child or fetus of a patient exposed to the molecule or study treatment regimen before conception or during pregnancy.
Medically significant:	The AE did not meet any of the above criteria, but could have jeopardized the patient and might have required medical or surgical intervention to prevent one of the outcomes listed above or involves suspected transmission via a medicinal product of an infectious agent.

## **Adverse Event Severity**

AE severity should be graded using the NCI CTCAE, version 4.03. These criteria are provided in the study manual.

AE severity and seriousness are assessed independently. 'Severity' characterizes the intensity of an AE. 'Serious' is a regulatory definition and serves as a guide to the sponsor for defining regulatory reporting obligations (see definition for Serious Adverse Events).

## **Relationship of the Adverse Event to Study Treatment**

The relationship of each AE to each study treatment (brentuximab vedotin, nivolumab) should be evaluated by the investigator using the following criteria:

Related:	There is evidence to suggest a causal relationship between the drug and the AE, such as: 

• an event that is uncommon and known to be strongly associated with drug exposure (e.g., angioedema, hepatic injury, Stevens-Johnson Syndrome)

• an event that is not commonly associated with drug exposure, but is otherwise uncommon in the population exposed to the drug (e.g., tendon rupture)

Unrelated:	Another cause of the AE is more plausible (e.g., due to underlying disease or occurs commonly in the study population), or a temporal sequence cannot be established with the onset of the AE and administration of the study treatment, or a causal relationship is considered biologically implausible

The Investigator's Brochures for brentuximab vedotin and nivolumab individually describe adverse events commonly observed relative to either agent (i.e., neutropenia or peripheral neuropathy with brentuximab vedotin; immune-mediated adverse events with nivolumab), as well as less common serious findings. The respective Investigator's Brochure should be referenced when attributing causality; however, the final decision regarding causality is at the discretion of the investigator.

### **7.6.1.2 Procedures for Eliciting and Recording Adverse Events**

Investigator and study personnel will report all AEs and SAEs whether elicited during patient questioning, discovered during physical examination, laboratory testing and/or other means by recording them on the CRF and/or SAE form, as appropriate.

#### **Eliciting Adverse Events**

An open-ended or non-directed method of questioning should be used at each study visit to elicit the reporting of AEs.

#### **Recording Adverse Events**

The following information should be recorded on the Adverse Events and Pre-existing Conditions CRF:

- Description including onset and resolution dates
- Whether it met serious criteria
- Severity
- Relationship to study treatment or other causality
- Outcome

#### **Diagnosis versus Signs or Symptoms**

In general, the use of a unifying diagnosis is preferred to the listing out of individual symptoms. Grouping of symptoms into a diagnosis should only be done if each component sign and/or symptom is a medically confirmed component of a diagnosis as evidenced by

standard medical textbooks. If any aspect of a sign or symptom does not fit into a classic pattern of the diagnosis, report the individual symptom as a separate AE.

Adverse reactions associated with the infusion of study drugs must be recorded as both the NCI CTCAE term for infusion-related reaction (e.g., cytokine release syndrome, acute infusion reaction, or allergic or hypersensitivity reaction) and with each sign or symptom recorded as an individual adverse event. Level of severity for both the overall infusion-related reaction term and the individual signs and symptoms should also be recorded.

### **Recording Serious Adverse Events**

For SAEs, record the event(s) on both the CRF and the SAE form.

The following should be considered when recording SAEs:

- Death is an outcome of an event. The event that resulted in the death should be recorded and reported on both an SAE form and CRF.
- For hospitalizations, surgical, or diagnostic procedures, the illness leading to the surgical or diagnostic procedure should be recorded as the SAE, not the procedure itself. The procedure should be captured in the narrative as part of the action taken in response to the illness.

### **Progression of the Underlying Cancer**

Do not use the term ‘disease progression’ alone when reporting AEs, including SAEs, because it is too nonspecific. Symptoms of disease progression that meet the criteria for an SAE must be reported. When possible, report the specific disease (clinical) manifestation of the progression (e.g., “malignant pleural effusion”, “spinal bone metastases”, “lymphadenopathy”, “brain metastases”). Otherwise, it is acceptable to report the specific disease (e.g., non-Hodgkin lymphoma) as an SAE.

### **Pregnancy**

**Notification to Drug Safety:** complete a Pregnancy Report Form for all pregnancies that occur from the time of first study drug dose until 6 months after the last dose of brentuximab vedotin or 8 months after the last dose of nivolumab, whichever is later, including any pregnancies that occur in the partner of a male study patient. Only report pregnancies that occur in a male patient’s partner if the estimated date of conception is after the male patient’s first study drug(s) dose. Email or fax to the sponsor’s Drug Safety Department within 48 hours of becoming aware of a pregnancy. All pregnancies will be monitored for the full duration; all perinatal and neonatal outcomes should be reported. Infants should be followed for a minimum of 8 weeks.

**Collection of data on the CRF:** all pregnancies (as described above) that occur within 6 months after the last dose of brentuximab vedotin or 8 months of the last dose of nivolumab, whichever is later, will also be recorded on the Adverse Events and Pre-Existing Conditions CRF.

Abortion, whether accidental, therapeutic, or spontaneous, should be reported as an SAE. Congenital anomalies or birth defects, as defined by the ‘serious’ criterion above (see definitions Section 7.6.1.1) should be reported as SAEs.

### **7.6.1.3 Reporting Periods for Adverse Events and Serious Adverse Events**

The safety reporting period for all AEs and SAEs is from study Day 1 (predose) through the EOT visit or 30 days after the last brentuximab vedotin dose or 100 days after the last nivolumab dose, whichever is later. However, all study protocol-related AEs are to be recorded from the time of informed consent. All SAEs that occur after the safety reporting period and are considered study treatment-related in the opinion of the investigator should also be reported to the sponsor.

SAEs will be followed until significant changes return to baseline, the event stabilizes (recovering/resolving) or is no longer considered clinically significant by the investigator, or the patient dies or withdraws consent. All non-serious AEs will be followed through the safety reporting period. Certain non-serious AEs of interest may be followed until resolution, return to baseline, or study closure.

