### **Efficacy Assessments**

Lymphoma response and progression will be assessed by investigators using the Lugano Classification Revised Staging System for malignant lymphoma ([Cheson 2014](#)). Dedicated CT scans of chest, neck, abdomen, and pelvis will be conducted at Cycle 2 response assessments. CT and PET scans will be performed at baseline, at EOT, prior to ASCT, and during long-term follow-up. PET will be performed with CT scans until the patient is in complete metabolic response (CmR) by PET. For patients in Part 3, investigators will conduct response assessments using the Lugano criteria with the incorporation of the Lymphoma Response to Immunomodulatory Therapy Criteria ([Cheson 2016](#)).

Cycle-2 CT scans of diagnostic quality will be performed 15 to 21 days after dosing to assess for progression of disease. The window for performing CT/PET scans at the EOT assessment for patients in Parts 1 and 2 is 23 to 37 days post last dose of study drug, but for patients in Part 3, the window for performing CT/PET scans at the EOT assessment is 15 to 30 days post last dose of study drug. Pre-ASCT scans may be waived for patients who have a scan performed within 6 weeks prior. Long-term follow-up assessments will be performed at the following timepoints post-ASCT (or post-EOT for patients who do not undergo ASCT): 100 days and then 6, 9, 12, 18, 24, 30, and 36 months, and then per institutional standard thereafter. A final safety visit will be performed 100 days after the last dose of nivolumab and after the EOT visit to assess for potential immune-mediated adverse events (AEs). Patients will be followed according to this schedule until withdrawal of consent, death, or study closure, whichever occurs first.

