### **5.5 Concomitant Therapy**

All concomitant medications, blood products, and radiotherapy administered will be recorded from Day 1 (predose) through the safety reporting period for brentuximab vedotin or 100 days after the patient's last dose of nivolumab, whichever occurs later. Any concomitant medication given for a study protocol-related AE should be recorded from the time of informed consent.

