# 6 STUDY ACTIVITIES

## 6.1 Schedule of Events

A schedule of events is provided in [Appendix A](#). Study activities are listed by visit in this section and descriptions of all study assessments are presented in Section [7](#).

AEs and concomitant medications will be recorded from Day 1 (predose) through 30 days after the last dose of brentuximab vedotin (see Section [7.6.1.3](#)) or 100 days after the last dose of nivolumab, whichever occurs later. Any study protocol-related AE should be recorded from the time of informed consent as well as any concomitant medications given for treatment of the AE.

All procedures on dosing days must be performed predose unless otherwise specified. Clinical laboratory assessments (serum chemistry panel, complete blood count [CBC] with differential [see Section [7.6.2](#)]), physical examination, and weight may be performed within 1 day prior to study drug administration. With the exception of gamma-glutamyl transpeptidase levels and thyroid function tests, the results from all other clinical laboratory assessments must be reviewed prior to study drug dosing.

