## 6.6 Safety Visit (100 days [+2 weeks] after last dose of nivolumab)

The final safety visit should occur 100 days after the last dose of nivolumab or 30–37 days post last dose of brentuximab vedotin (EOT visit), whichever is later. The following assessments will be performed:

- Physical examination, including assessment for potential immune-mediated adverse events
- Serum chemistry panel (see Section 7.6.2)
- CBC with differential (see Section 7.6.2)
- Blood samples for ATA assessments

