7.6.3 Deaths

Summaries of deaths will be presented by dose regimen and overall. Deaths that occur within the safety reporting period (i.e., within 30 days of last study treatment with brentuximab vedotin or 100 days of nivolumab, whichever is later) will be presented, as well as deaths that occur beyond this time point. In addition, primary cause of death will be summarized by descending MedDRA preferred term (unless otherwise specified) and summarized by dose regimen and overall. Death information will be listed by patient.

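### AE and concomitant-medication collection usually ends 100 days after the last nivolumab dose, but the final safety visit may fall as late as day 114, so new non-serious or unrelated events on days 101 to 114 need not be recorded

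*Protocol*

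**What the plan says.** **End of collection.** Protocol 7.6.1.3 closes the safety reporting period at the latest of three points: "through the EOT visit or 30 days after the last brentuximab vedotin dose or 100 days after the last nivolumab dose, whichever is later". Section 6.1 states that "AEs and concomitant medications will be recorded from Day 1 (predose) through 30 days after the last dose of brentuximab vedotin", with the alternative "or 100 days after the last dose of nivolumab, whichever occurs later". Section 5.5 records concomitant therapy "through the safety reporting period for brentuximab vedotin or 100 days after the" last nivolumab dose, again taking the later date. The schedules in Appendix A collect AEs and medications up to the end of the safety reporting period and set no date of their own.

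**Final safety visit.** Section 6.6 is headed "Safety Visit (100 days [+2 weeks] after last dose of nivolumab", so its tolerance is on the plus side only. Its text adds that the visit is held at the EOT visit, 30 to 37 days after the last brentuximab vedotin dose, if that is later. The visit includes a physical examination for immune-mediated events, serum chemistry and a CBC. The Synopsis places it "after the EOT visit to assess for potential immune-mediated adverse events".

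**After the period closes.** Under 7.6.1.3 only SAEs that the investigator judges related to treatment must still be reported. Non-serious AEs are followed to the end of the period, with optional longer follow-up for certain events of interest.

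**SAP.** Section 7.6.3 defines the safety reporting period for deaths as "within 30 days of last study treatment with brentuximab vedotin or 100 days of nivolumab, whichever is later", and also presents deaths after it.

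**The concern.** The sentence in 7.6.1.3 names the EOT visit as a possible end point. A visit 37 days after the last dose is therefore covered even though the brentuximab vedotin limit is 30 days. The later visit, which exists to look for immune-mediated toxicity, has no such clause, and the protocol gives no reason for leaving it out.

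The visit's own tests can generate the affected events. The chemistry panel in 7.6.2 includes ALT, AST, amylase and lipase, and 7.6.1.1 makes an abnormal value recordable if, for example, it requires intervention. Suppose such an abnormality first arises at a day 110 visit and a corticosteroid is started. As written, neither the AE nor the steroid has to be recorded, unless the event is an SAE judged related.

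Type, incidence and severity of AEs are a primary endpoint. SAP 7.6.1.1 lists immune-related AEs among those that may be of special importance. SAP 7.6.2 summarises concomitant medications in patients who have them. SAP 7.6.1.2 presents laboratory results only through the EOT visit, so an AE record is the main route by which a finding at the safety visit reaches the analysis.

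**Working it through.** The plan states no figure to reproduce. The check is date arithmetic on its own schedule.

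**Inputs**
- Four 21-day cycles. Brentuximab vedotin falls on study days 1, 22, 43 and 64. Nivolumab falls on days 8, 22, 43 and 64 (Parts 1 and 2) or 1, 22, 43 and 64 (Part 3) (Protocol 3.1.1, 3.1.2).
- EOT visit: 30 to 37 days after the last dose of study drug (6.4).
- End of period: 7.6.1.3. Visit window: 6.6.
- Assumptions: no dose delays, and brentuximab vedotin continued to cycle 4 (day 64) even when nivolumab stops earlier.

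**Formulas** (N = study day of last nivolumab dose, B = study day of last brentuximab vedotin dose = 64)
- End of period = max(EOT visit, B + 30, N + 100)
- Latest visit day = N + 114
- Largest gap = (N + 114) − end of period

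In every case B + 30 = 94, and the EOT visit falls on days 64 + 30 = 94 to 64 + 37 = 101.

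| Part | Last nivolumab cycle | N | End of period | Visit window | Largest gap (days) |
|---|---|---|---|---|---|
| 1 and 2 | 1 | 8 | 108 | 108–122 | 14 |
| 1 and 2 | 2 | 22 | 122 | 122–136 | 14 |
| 1 and 2 | 3 | 43 | 143 | 143–157 | 14 |
| 1 and 2 | 4 | 64 | 164 | 164–178 | 14 |
| 3 | 1 | 1 | 101 | 101–115 | 14 |
| 3 | 2 | 22 | 122 | 122–136 | 14 |
| 3 | 3 | 43 | 143 | 143–157 | 14 |
| 3 | 4 | 64 | 164 | 164–178 | 14 |

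The nivolumab limit sets the end of the period in all eight cases. The closest is Part 3 with nivolumab stopped after cycle 1, where the latest EOT visit (day 101) ties with N + 100 = 101.

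**When the gap disappears.** For the EOT visit to fall after N + 100, B must exceed N by more than 100 − 37 = 63 days, or the EOT visit must be delayed for an AE, which 6.4 allows. Without delays the largest possible difference is 64 − 1 = 63 days. When the EOT visit is the later date, 6.6 makes it the final safety visit and 7.6.1.3 already covers it, so the gap is zero.

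**What falls in the gap** (days counted from the last nivolumab dose)

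| Event | Required to be recorded? |
|---|---|
| Onset by day 100, found on days 101–114 | Yes: 7.6.1.3 turns on when an event occurs |
| SAE on days 101–114, judged related | Yes: reported without time limit |
| SAE on days 101–114, judged unrelated | No |
| Non-serious AE with onset or worsening on days 101–114 | No |
| Medication started for either unrecorded event | No |

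**Relative length.** For a fully treated patient, 14 days set against 164 days of collection is 14/164 = 8.5%, and only if the visit takes place on the last permitted day.

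**After the fix.** Adding the visit date to the maximum brings the largest gap from 14 days to 0.

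**The case against.** The strongest reply is that the mismatch is small and that a fixed limit has merit. Day 100 is the target and the two weeks are tolerance. A visit at or after day 100 is a sensible way to look back over the whole period. A limit of 100 days after nivolumab is normally the same for everyone, whereas a limit tied to the visit varies with booking. Related SAEs are reported whenever they occur. The treatment-emergent rule in SAP Appendix B has no end date, so a late event that a site does record will be counted. All of this stands. It limits the size of the problem and means that the fault lies in collection, not in the analysis rule. It does not explain why the period extends to one visit and not to the other.

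A reader might infer more than the documents support:
- **That everything first found at the visit is lost.** It is not. An event with onset by day 100 stays recordable whenever it is found.
- **That 93% of visits or events are affected.** The window has 15 permitted days (100 to 114), of which 14 lie after day 100, and 14/15 = 93%. That counts calendar days. Nothing suggests that visits spread evenly over them, and it says nothing about events.
- **That about 92 patients lose data.** The planned enrolment is only a ceiling on the number exposed to the gap.
- **That the site's booking day changes what is collected.** As written, the limit is normally fixed. It is the remedy that introduces variation.
- **That deaths are lost under SAP 7.6.3.** That section also presents deaths beyond the period.

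**Conclusion.** The mismatch is real and narrow. In the usual case, up to 14 days per patient (days 101 to 114 after the last nivolumab dose) can pass between the close of required collection and the final safety visit. Non-serious AEs and SAEs judged unrelated that begin or worsen in that interval, including laboratory abnormalities first arising at the visit, need not be recorded, nor need the medication started for them.

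This rests on three conditions: the nivolumab limit governs, as it does in all eight no-delay cases; the visit is held after day 100; and an abnormality first seen at the visit, with no earlier sign, is given that day as its onset. The number of events lost cannot be derived, because the documents give neither a rate of late events nor a distribution of visit dates. The case for change is that the correction is cheap and concerns a primary safety endpoint. The documents do not show a material bias.

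**What to change.** In Protocol 7.6.1.3, add completion of the final safety visit (Section 6.6) as a fourth item in the list from which the latest date is taken. Use the same end point in 5.5 and 6.1, preferably by reference to 7.6.1.3 so that the three sections cannot diverge. If the visit is not held, the three existing limits apply. Appendix A needs no edit, because it already refers to the reporting period. SAP 7.6.3 needs no change to recover data; its definition should be aligned only for consistency.

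The cost is one clause in three protocol sections and up to 14 more days of AE and medication recording per patient, closed at a visit already scheduled. The drawback is a reporting period that varies by up to 14 days between patients within the permitted window. To keep a common observation length, AE summaries can also be shown truncated at day 100 after the last nivolumab dose.
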